**Table 16-5 Management of immune related skin toxicity**

CTCAE v5.0 Grade	KN046 Dosing Management	Action and Guidelines	Diagnostic Consideration
Grade 1-2 
 
• Skin rash, with or without symptoms, <30% body surface area (BSA)
 
	
 
• No change in KN046 dose
 
	
 
• Symptomatic treatment 
 
• Topical corticosteroids, eg betamethasone 0.1% cream or hydrocortisone 1%)
 
• Urea-containing creams in combination with oral antipruritics (eg, diphenhydramine HCl or hydroxyzine HCl)
 
 
 
• At investigator's discretion, treatment with oral steroids for Grade 2 events
 
• Treat as Grade 3 skin toxicity if Grade 2 skin toxicity accompanies apparent clinical signs and symptoms
 
	All attempts should be made to rule out other causes such as metastatic disease, infection or allergic dermatitis
Grade 3 
 
• Rash covers >30% BSA or Grade 2 with substantial symptoms
 
	
 
• Withhold KN046 treatment
 
	
 
• Dermatology consultation. Consider biopsy to confirm diagnosis
 
• Recommend oral steroids treatment, starting with prednisone 1 mg/kg/day or equivalent. When
 
	

		
symptoms improve to Grade 1 or less, steroid taper should be started and continued over no less than 4 weeks
	
Grade 4 

• Skin sloughing >30% BSA with associated symptoms (eg, erythema, purpura, epidermal detachment)

	

• Discontinue KN046

	

• Dermatology consultation. Consider biopsy and clinical dermatology photograph

• Initiate steroids at methylprednisolone 1~2 mg/kg/day or equivalent. When symptoms improve to Grade 1 or less, steroid taper should be started and continued over no less than 4 weeks

	

**Table 16-6 Management of immune related nephritis**

CTCAE v5.0 Grade	KN046 Management	Dosing	Action and Guidelines	Diagnostic Consideration
Grade 1 • Creatinine 1.5 x baseline or > ULN~1.5 x ULN	
 
No change in KN046 dose
 
Withhold KN046 if event does not improve with symptomatic treatment
 
		
 
Symptomatic treatment
 
Monitor creatinine weekly; resume routine creatinine monitoring per protocol when it returns to baseline
 
	All attempts should be made to rule out other causes such as obstructive uropathy, progression of disease, or injury to other medications
Grade 2 • Creatinine > 1.5~3 x baseline or > 1.5~3 x ULN	
 
Withhold KN046 treatment
 
Discontinue KN046 treatment if elevations persists > 7 days or worsen after appropriate medical interventions
 
		
 
Renal consultation. Consider ultrasound and/or biopsy as appropriate
 
Treat with systemic corticosteroids at a dose of prednisolone 1~2 mg/kg/day or equivalent. When symptoms improve to Grade 1 or less, steroid taper should be started and continued over no less than 4 weeks
 
If elevations persist > 7 days or worsen, treat as Grade 3 or 4
 
	
Grade 3-4 • Creatinine > 3 x baseline or >3 x ULN	
 
Discontinue KN046
 
		
 
Renal consultation. Consider ultrasound and/or biopsy as appropriate
 
Monitor creatinine daily
 
Treat with systemic corticosteroids at a dose of prednisolone 1~2 mg/kg/day or equivalent. When symptoms improve to Grade 1 or less, steroid taper should be started and continued over no less than 4 weeks
 
	

**Table 0** Management of immune related myocarditis

CTCAE v5.0 Grade	KN046 Dosing Management	Action and Guidelines	Diagnostic Consideration
Grade 1 

Abnormal in cardiac tests (eg, myocardial enzymes, ECG)

	

Discontinue KN046

	

Cardiology consultation

Exam ECG, troponin, BNP, cardiac ultrasound and chest X-ray

Immediately initiate high-dose steroid treatment

Prednisolone 1~2 mg/kg/day or equivalent

Increase steroid dose (eg, methylprednisolone 1 g/day) and add in infliximab, mycophenolate mofetil or anti-thymocyte globulin if symptoms do not promptly respond to steroids

Treat cardiovascular symptoms according to ACC/AHA guidelines

Subjects with troponin or conduction abnormalities requires to be treated within cardiac ICU

	All attempts should be made to rule out myocardial infarction, viral myocarditis, infectious heart valve disease etc
Grade 2 

Abnormal in cardiac tests with mild symptoms

			
Grade 3-4 

Moderate to severe cardiac dysfunction requiring intravenous treatment or life-threatening

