## 7.3 Dose modifications

KN046 will be withheld for  $\geq$  Grade 3 drug-related toxicity, including laboratory abnormalities with the exception of laboratory abnormalities that are not clinically significant or that do not meet the criteria of adverse event, and severe or life-threatening AEs (i.e. anemia grade 3, lymphocytopenia grade 3-4, hypercholesterolemia grade 3-4, hypertriglyceridemia grade 3-4).

If a dose of KN046 is withheld due to toxicity, subjects may resume dosing with KN046 when toxicity has improved to  $\leq$  Grade 1.

In case toxicity does not resolve to Grade 0-1 within 12 weeks after last infusion, trial treatment will be discontinued. With the agreement between investigator and Sponsor Medical Monitor, subjects with a laboratory adverse event at Grade 2 after 12 weeks may continue treatment only if asymptomatic and controlled, for example, hypothyroidism or Type 1 diabetes controlled by replacement treatments.

Subjects who require corticosteroids to manage drug-related adverse events must be at an equivalent dose of  $\leq 10$  mg per day of prednisone to resume dosing with KN046. In case of an inability to reduce the corticosteroid dose for managing a drug-related adverse event to the equivalent of  $\leq 10$  mg prednisone per day within 12 weeks of last KN046 dose, patient will go off treatment.

For a subject who experiences a recurrence of the same serious adverse event at the same grade or greater after rechallenge of KN046, study medication will be discontinued.

In addition, if any of below drug-related adverse events occur, KN046 treatment will be permanently discontinued:

- $\geq$  Grade 3 immune related pneumonitis;
- Recurrence of  $\geq$  Grade 2 immune related pneumonitis lasting  $\geq$  4 weeks after appropriate medical interventions;
- $\geq$  Grade 2 immune related CNS toxicities lasting  $\geq$  4 weeks after appropriate medical interventions;
- $\geq$  Grade 3 immune related colitis;
- $\geq$  Grade 3 uveitis or optic neuritis;
- $\geq$  Grade 3 immune related hepatitis with ALT/AST  $> 8 \times$  ULN OR TBIL  $> 3 \times$  ULN;
- $\geq$  Grade 3 immune related nephritis or renal dysfunction.
- $\geq$  Grade 2 myocarditis
- $\geq$  Grade 2 myositis

**Table 7-1** *Guideline on KN046 dose modification*

Toxicity	Grade	Withheld treatment	Resume treatment	Dose / schedule for resuming treatment	Discontinuation of treatment
Hematological toxicity	1, 2	No	Not applicable	Not applicable	Not applicable

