	3 (except for isolate event of grade 3 neutropenia)	Yes			

Toxicity	Grade	Withheld treatment	Resume treatment	Dose / schedule for resuming treatment	Discontinuation of treatment
	4	Yes	Toxicity resolves to $\leq$ Grade 1 or baseline within 12 weeks of last KN046 dose	Resume at planned dose and increase the dose interval by 1 week at each occurrence	Permanent discontinuation if toxicity does not resolve to $\leq$ Grade 1 or baseline within 12 weeks of last KN046 infusion
Non-hematological toxicity with the exception for alopecia of any Grade and Grade 2 fatigue which will be treated as Grade 1 adverse reaction (with the exception of those reported in 7.3)	1	No	Not applicable	Not applicable	Not applicable
	2	Yes	Toxicity resolves to $\leq$ Grade 1 or baseline within 4 weeks of last KN046 dose	Resume at planned dose and dose interval	Permanent discontinuation if toxicity does not resolve to $\leq$ Grade 1 or baseline within 12 weeks of last KN046 infusion
			Toxicity resolves to $\leq$ Grade 1 or baseline beyond 4 weeks and within 12 weeks of last KN046 dose	Resume at planned dose and increase the dose interval by 1 week at each occurrence	
	3, 4	Yes	Toxicity resolves to $\leq$ Grade 1 or baseline within 12 weeks of last KN046 dose	Resume at planned dose and increase the dose interval by 1 week at each occurrence	Permanent discontinuation if toxicity does not resolve to $\leq$ Grade 1 or baseline within 12 weeks of last KN046 infusion; Permanent discontinuation should also be considered for any life-threatening or severe adverse reactions

Note: if increased Grade 3 or 4 CPK occurs, myocardial enzymes (CPK, CK, Tn1, TnT) should also be measured. KN046 will be permanently discontinued in case of elevation on treatment-related myocardial enzymes
					

Infusion related reactions, hypersensitivity reactions, and immune related adverse event should be handled according to the guidelines provided in Sections 7.5.1 and Appendix A, respectively.

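### Section 7.3 and Appendix A set different discontinuation thresholds for the same immune-related events, most clearly hepatitis, and no order of precedence is stated

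*Combined protocol and SAP*

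**What the plan says.** Section 7.3 (Dose modifications) introduces its list of permanent stops with "In addition, if any of below drug-related adverse events occur, KN046 treatment will be permanently discontinued". Four entries matter here, and each grade carries an at-or-above sign:

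- "Grade 2 myocarditis".
- "Grade 3 immune related hepatitis with ALT/AST" above 8 x ULN or total bilirubin above 3 x ULN.
- "Grade 3 immune related nephritis or renal dysfunction".
- Recurrence of at least "Grade 2 immune related pneumonitis lasting" 4 weeks or more despite treatment.

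For doses held because of toxicity, the general text of 7.3 says that "subjects may resume dosing with KN046 when toxicity has improved to" Grade 1 or below. Table 7-1 adds detail. A Grade 3-4 non-hematological event that recovers within 12 weeks may resume at the planned dose with the interval lengthened by a week. A Grade 1 event needs no hold. The sentence after the table says that "immune related adverse event should be handled according to the guidelines provided in Sections 7.5.1 and Appendix A, respectively".

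Appendix A sets its own stops:

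- Hepatitis: ALT or AST above 5 x ULN, whatever the bilirubin.
- Myocarditis: from Grade 1, described as "Abnormal in cardiac tests (eg, myocardial enzymes, ECG" and so on, with immediate high-dose steroids.
- Nephritis: Grade 3-4, or Grade 2 if the rise lasts more than 7 days or worsens despite treatment.
- Pneumonitis: Grade 3-4; a second episode of Grade 2 or higher on rechallenge; or Grade 2 lasting 4 weeks or more.

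**The concern.** These rules decide whether an individual patient is exposed again to a drug suspected of causing an immune toxicity. Section 7.3 does not leave irAE stops to the appendix: its bullets set thresholds for events that it calls immune-related. Two sets of numbers therefore apply to the same event. If Appendix A governs, the 8 x ULN condition in 7.3 has no function. If 7.3 governs, the 5 x ULN stop in Appendix A is not binding. The appendix also describes itself as general principles, whereas the 7.3 list is worded as mandatory, so status alone does not settle the question.

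The schedule is built to find early change. Troponin is tested at least on Day 1 of each cycle, and cardiac ultrasonography is done at C2D1, C2D15 and C3D1 (sections 6.1.2.1 and 6.1.2.2). Abnormal cardiac tests without symptoms could therefore come to light, and staff need one answer when they do.

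**Working it through.** No design figure is involved, so the check sets the texts side by side.

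| Event | 7.3 list | If not on the 7.3 list (Table 7-1) | Appendix A | Where they differ |
|---|---|---|---|---|
| Hepatitis | Grade 3+ with ALT/AST >8 x ULN or TBIL >3 x ULN | Grade 3-4: hold, resume after recovery within 12 weeks | Stop at ALT/AST >5 x ULN | ALT/AST above 5 and up to 8 x ULN, TBIL not above 3 x ULN |
| Myocarditis | Grade 2+ | Grade 1: no hold, subject to the enzyme note | Stop from Grade 1 | Grade 1, mainly ECG or imaging change |
| Nephritis | Grade 3+ | Grade 2: hold, resume after recovery within 12 weeks | Also stop Grade 2 lasting >7 days or worsening | Grade 2 (creatinine >1.5 to 3 x), persistent or worsening |
| Pneumonitis, Grade 2 | Recurrence and duration of 4+ weeks, joined | Hold, resume after recovery within 12 weeks | Recurrence or duration of 4+ weeks, either | One condition met without the other |

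**Hepatitis.** Take an immune-related event peaking at 6 x ULN with bilirubin not above 3 x ULN. It misses the 7.3 list because 6 is below 8. Table 7-1 then allows resumption after recovery, although it also asks that permanent discontinuation be considered for severe reactions. Appendix A discontinues because 6 is above 5.

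**Myocarditis.** The note under Table 7-1 permanently stops KN046 for treatment-related elevation of myocardial enzymes, and that sentence has no grade floor. It follows a sentence about Grade 3 or 4 CPK. On a wide reading, the note already covers enzyme-based Grade 1 events. On a narrow reading, a troponin rise without Grade 3-4 CPK stays outside it. An isolated ECG or imaging change is outside it on either reading.

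**Size.** The only relevant counts are the Grade 3 or higher hepatic rows at 5 mg/kg Q2W. Table 2-4 (N = 30) prints one ALT increase and one abnormal hepatic function, which is 1 subject if they are the same person and 2 if not. Table 2-10 (N = 45) shows no Grade 3 or higher irAE at that dose. Expected numbers among 29 patients are:

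- pooled (30 + 45 = 75): 29 x 1/75 = 0.39 to 29 x 2/75 = 0.77;
- first trial alone: 29 x 1/30 = 0.97 to 29 x 2/30 = 1.93.

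These counts cover all Grade 3 or higher hepatic irAEs in the printed rows. Only the share between 5 and 8 x ULN falls in the gap, and that share is not printed. The rows in Table 2-4 are also incomplete: at 10 mg/kg, 3 subjects had a Grade 3 or higher irAE, but no printed row shows one. For the same reason, the absence of a myocarditis row does not show that the rate is zero.

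**The case against.** The strongest reply is that the protocol already routes irAEs to Appendix A. Section 7.3 says so after Table 7-1, section 7.5 repeats it, and 2.4.1.1 also points there. Following Appendix A breaks no 7.3 bullet, because the list never says that an unlisted event may continue. The resumption sentence is permissive and concerns held doses, so it need not restart a patient whom the appendix has discontinued. Much of this stands: the texts can be reconciled by treating 7.3 as a minimum. But the protocol does not say so, and that reading leaves the 8 x ULN clause without effect.

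A reader might infer more than the documents support:

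- *That 7.3 requires dosing to continue at Grade 1 myocarditis.* It does not. The list is additive, the enzyme note may already stop treatment, and irAEs are referred to Appendix A. Myocarditis is a narrower difference than hepatitis.
- *That the hepatic gap has already occurred.* Section 2.3.2.1.1 reports a Grade 3 hepatic abnormality without bilirubin increase at 5 mg/kg Q2W, but gives no ALT/AST value. Nothing places that subject between 5 and 8 x ULN.
- *That Appendix A is stricter in nearly every table.* A tally depends on the criterion. Colitis and pneumonitis both match 7.3 at Grade 3 or higher, and for Grade 2 pneumonitis only the recurrence and duration wording differs. Grade 4 skin toxicity is not on the 7.3 list, but Table 7-1 asks that permanent discontinuation be considered for life-threatening events. The nephritis difference is conditional, not a uniform shift of one grade.

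**Conclusion.** The point holds as a mismatch between two stopping rules with no stated precedence. It is clear for hepatitis between 5 and 8 x ULN. It is smaller for Grade 1 myocarditis, for persistent or worsening Grade 2 nephritis, and for Grade 2 pneumonitis. It is worth correcting because it governs re-exposure of individual patients and is cheap to correct. It does not touch the Simon design, the sample size or the primary endpoint. The number of patients in the gap cannot be estimated from the documents. Judging it probably small assumes that Grade 3 or higher hepatic irAEs occur about as often as the incomplete phase I rows suggest, and that only some of them peak between 5 and 8 x ULN.

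**What to change.** In 7.3, state that Appendix A governs discontinuation for the irAEs it tabulates, and that the 7.3 list continues to apply to events it does not tabulate (uveitis or optic neuritis, CNS toxicity, myositis). Then align three bullets:

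- hepatitis: ALT/AST above 5 x ULN whatever the bilirubin;
- myocarditis: any grade;
- nephritis: Grade 3 or higher, or Grade 2 that lasts more than 7 days or worsens.

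The precedence sentence settles the pneumonitis wording.

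Leave the enzyme sentence in the Table 7-1 note tied to the Grade 3-4 CPK trigger. Detaching it may look like the natural way to close the myocarditis gap. But the note counts CPK among the myocardial enzymes, so a mild treatment-related CPK rise could become a permanent stop, at odds with the Grade 2 threshold for myositis.

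The cost is a few lines of text, with no new tests or visits. The downside is that a few patients who might have resumed would stop, in a setting where section 2.3.1 says there is no standard of care after checkpoint inhibitor failure.
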